1.2 Consultation history. Have you consulted with anyone at HSD about this study?

It is not necessary to obtain advance consultation. If you have: answering this question will help ensure that the IRB is aware of and considers the advice and guidance you were provided.

→ If yes, briefly describe the consultation: approximate date, with whom, and method (e.g., by email, phone call, in-person meeting).

(1.3) Similar and/or related studies. Are there any related IRB applications that provide context for the proposed activities?

Examples of studies for which there is likely to be a related IRB application: Using samples or data collected by another study; recruiting subjects from a registry established by a colleague's research activity; conducting Phase 2 of a multi-part project, or conducting a continuation of another study; serving as the data coordinating center for a multi-site study that includes a UW site.

Providing this information (if relevant) may significantly improve the efficiency and consistency of the IRB's review.

→ If yes, briefly describe the other studies or applications and how they relate to the proposed activities. If the other applications were reviewed by the UW IRB, please also provide: the UW IRB number, the study title, and the lead researcher's name.

Our other two studies, Ultrasonic Propulsion of Kidney Stones (STUDY00002792) and Propulsion 2 (STUDY00002899), use the same investigational device. In this study, the device is used for imaging only

1.4 Externally-imposed urgency or time deadlines. Are there any externally-imposed deadlines or urgency that affect your proposed activity?

HSD recognizes that everyone would like their IRB applications to be reviewed as quickly as possible. To ensure fairness, it is HSD policy to review applications in the order in which they are received. However, HSD will assign a higher priority to research with externally-imposed urgency that is beyond the control of the researcher. Researchers are encouraged to communicate as soon as possible with their HSD staff contact person when there is an urgent situation (in other words, before submitting the IRB application). Examples: a researcher plans to test an experimental vaccine that has just been developed for a newly emerging epidemic; a researcher has an unexpected opportunity to collect data from students when the end of the school year is only four weeks away.

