HSD may ask for documentation of the externally-imposed urgency. A higher priority should not be requested to compensate for a researcher's failure to prepare an IRB application in a timely manner. Note that IRB review requires a certain minimum amount of time; without sufficient time, the IRB may not be able to review and approve an application by a deadline.

)	No	
	Yes	→ If yes, briefly describe the urgency or deadline as well as the reason for it.

1.5 Objectives Using lay language, describe the purpose, specific aims, or objectives that will be met by this specific project. If hypotheses are being tested, describe them. You will be asked to describe the specific procedures in a later section.

If your application involves the use of a HUD "humanitarian" device: describe whether the use is for "on-label" clinical patient care, "off-label" clinical patient care, and/or research (collecting safety and/or effectiveness data).

Specific questions this research project is designed to answer:

- 1. How well are stones of different types seen by two standard ultrasound techniques (B-mode and Doppler)?
- 2. How accurate is the measurement of stone size on ultrasound?
- 3. How accurate is ultrasound at detecting stones?
- 4. Can ultrasound reliably detect stones smaller than 2 mm?
- 5. How much do stones and stone pieces move during lithotripsy treatment?

1.6 Study design. Provide a one-sentence description of the general study design and/or type of methodology.

Your answer will help HSD in assigning applications to reviewers and in managing workload. Examples: a longitudinal observational study; a double-blind, placebo-controlled randomized study; ethnographic interviews; web scraping from a convenience sample of blogs; medical record review; coordinating center for a multi-site study.

Observational study examining the accuracy of ultrasound imaging.

(1.7) Intent. Check all the descriptors that apply to your activity. You must place an "X" in at least one box.

This question is essential for ensuring that your application is correctly reviewed. Please read each option carefully.
Descriptor
1. Class project or other activity whose purpose is to provide an educational experience for the researcher (for example, to learn about the process or methods of doing research).
2. Part of an institution, organization, or program's own internal operational monitoring.
le l

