Example: A school district may require you to obtain permission from the head district office as well as school principals before approaching teachers or students; a factory in China may allow you to interview factory workers but not allow you to pay them.

N/A There are no local administrative or ethical requirements that are affecting our research currently.

4 RECRUITING and SCREENING PARTICIPANTS

4.1 Recruiting and Screening. Describe how you will identify, recruit, and screen subjects. Include information about: how, when, where, and in what setting. Identify who (by position or role, not name) will approach and recruit subjects, and who will screen them for eligibility.

The research team pre-screens medical records of patients at the UW Urology clinic and the UW Kidney Stone Center for Kidney Stones at Northwest Hospital for study eligibility. As the clinics have become increasingly busy and his patient load continues to grow, the ability to pre-screen the medical records allows the research staff to inform him of eligible patients, which makes his work load for the study easier. The study team may attempt to contact patients by phone before their visits to gauge interest in the study using the approved talking points. If a member of the study team is able to speak with a patient, they describe the study to them if they are interested.

Drs. [name], [name], and [name] inquire if eligible patients at their clinic visits are interested in participating in a research study. If a patient is interested, a member of the study team will discuss the consent form with that person. However, as clinic has become increasingly busy and his patient load continues to grow, the ability to prescreen the medical records allows the research staff to inform him of eligible patients, which makes his work load for the study easier.

4.2 Recruitment materials.

a. What materials (if any) will you use to recruit and screen subjects?

Examples: talking points for phone or in-person conversations; video or audio presentations; websites; social media messages; written materials such as letters, flyers for posting, brochures, or printed advertisements; questionnaires filled out by potential subjects.

We have talking points for phone conversations for pre-screening patients.

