5 PROCEDURES

(5.1) Study procedures. Using lay language, provide a complete description of the study procedures, including the sequence, intervention or manipulation (if any), time required, and setting/location. If it is available and you think it would be helpful to the IRB: Upload a study flow sheet or table to the **Supporting Documents** SmartForm in **Zipline**.

For studies comparing standards of care: It is important to accurately identify the research procedures. See UW IRB POLICY:
Risks of Harm from Standard Care and the draft guidance from the federal Office of Human Research Protections, "Guidance on Disclosing Reasonably Foreseeable Risks in Research Evaluating Standards of Care"; October 20, 2014.

Patients presenting to the UW Urology clinic or Kidney Stone Center with at least one kidney stone or who are being treated for nephrolithiasis (kidney and ureteral stones) and undergoing surgery for stones (shock wave lithotripsy, ureteroscopy, or percutaneous nephrolithotomy) to manage their stones will be screened for this study. Those who meet the study criteria and indicate initial willingness to participate to the clinical staff will be approached by research staff. The research staff will explain the study and obtain informed consent.

Group 1 – Subjects with kidney stones

- The first group consists of awake, not anaesthetized subjects with kidney stones. In this group, we
 want to look at how well ultrasound sees and sizes the stone, tested by comparison to CT in their
 medical record.
- Existing CT, x-ray, ultrasound, or fluoroscopy images of the stone will be saved from the medical record.
- The subjects will be awake during the imaging. They will be offered an examination gown during imaging and may be asked to roll to different positions for improved imaging or so that both kidneys may be imaged. These subjects may be asked to hold their breath for up to 10 seconds during imaging.
- We place a water-based gel and ultrasound probe against the subject's skin on the back, sides, and abdomen. We will image the kidney, ureter, and/or bladder with B-mode and Doppler ultrasound. Images will be saved. Audio annotation for the ultrasound images will be saved.

_

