- ** If you checked the box about radio-isotopes: you are responsible for informing in advance all appropriate clinical personnel (e.g., nurses, technicians, anesthesiologists, surgeons) about the administration and use of the radio-isotope, to ensure that any personal safety issues (e.g., pregnancy) can be appropriately addressed. This is a condition of IRB approval.
- **10.5 Data and Safety Monitoring**. A Data and Safety Monitoring Plan (DSMP) is required for clinical trials (as defined by NIH). If required for your research, upload your DSMP to the **Supporting Documents** SmartForm in **Zipline**. If it is embedded in another document you are uploading (for example, a Study Protocol, use the text box below to name the document that has the DSMP.

N/A

10.6 Un-blinding. If this is a double-blinded or single-blinded study in which the participant and/or you do not know the group to which the participant is assigned: describe the circumstances under which un-blinding would be necessary, and to whom the un-blinded information would be provided.

N/A

- **10.7 Withdrawal of participants.** If applicable, describe the anticipated circumstances under which participants will be withdrawn from the research without their consent. Also, describe any procedures for orderly withdrawal of a participant, regardless of the reason, including whether it will involve partial withdrawal from procedures and any intervention but continued data collection or long-term follow-up.
 - Subjects may also be discontinued by the study coordinator or physician because of an adverse event or other event related to the subject's health or welfare. Subjects may be discontinued from the study because their stone could not be identified on ultrasound. Subjects discontinued prior to the investigational treatment will not be counted as an enrollment and no further data will be collected.
- **10.8** Anticipated direct benefits to participants. If there are any direct research-related benefits that some or all individual participants are likely to experience from taking part in the research, describe them below:

Do not include benefits to society or others, and do not include subject payment (if any). Examples: medical benefits such as laboratory tests (if subjects receive the results); psychological resources made available to participants; training or education that is provided.

None

- 10.9 Individual subjects findings.

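### Section 10.7 lets a subject leave the study because the stone was not seen on ultrasound, with an undefined cut-off for who still counts, so missed stones can drop out of the detection analysis

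*Protocol*

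**What the plan says.** Section 1.5 lists the study questions. Question 3 is "How accurate is ultrasound at detecting stones", and question 4 asks whether stones under 2 mm can be detected reliably. Section 1.6 describes an observational study of imaging accuracy.

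Section 5.1 gives the comparators. For Group 1 (awake subjects) the investigators "want to look at how well ultrasound sees and sizes the stone, tested by comparison to CT in their" medical record. For Group 2 (anaesthetized surgical subjects) the comparator is what is observed at surgery.

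Section 10.7 covers withdrawal and contains two sentences that matter here: "Subjects may be discontinued from the study because their stone could not be identified on ultrasound" and "Subjects discontinued prior to the investigational treatment will not be counted as an enrollment and no further data will be collected". Section 1.3 distinguishes this study from two related propulsion studies that use the same device: "In this study, the device is used for imaging only".

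On the order of ultrasound and CT, the form for section 5.1 asks the applicant to "provide a complete description of the study procedures, including the sequence, intervention or manipulation (if any), time required, and setting/location". The Group 1 answer has an early item, "Existing CT, x-ray, ultrasound, or fluoroscopy images of the stone will be saved from the medical" record, and then describes the scan. Section 4.1 says: "The research team pre-screens medical records of patients at the UW Urology clinic". No section says whether the ultrasound detection call is made before or after the CT is seen.

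**The concern.** Sensitivity is the share of stones present on the comparator that ultrasound finds. A subject whose stone is present but not identified on ultrasound is a false negative. Section 10.7 makes exactly that outcome a permitted reason to leave the study, then ties whether the subject counts to a treatment that the study does not give. If such subjects leave the data, the denominator loses misses and keeps detections. Questions 3 and 4 would then be answered partly by a withdrawal rule instead of by the imaging.

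An analysis plan may be unable to repair this later. It can analyse only subjects who were counted and whose comparator was collected. The risk is most concrete in Group 2. Imaging takes place during the procedure and the comparator comes from surgery, so stopping data collection once the stone is not seen could mean that the comparator is never recorded.

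A lesser matter is that nothing places the Group 1 detection call before sight of the CT. A call made with the CT in view would also tend to raise sensitivity.

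**Working it through.** The protocol states no expected sensitivity, no discontinuation rate and no sample-size calculation, so there is no figure to reproduce. The check sets the passages side by side and then establishes direction and limit.

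**Step 1. What the cut-off can mean.** Section 10.7 refers to a point before the investigational treatment; section 1.3 says the device only images. Three readings are open:

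- There is no such treatment, so every discontinued subject is before it. All are uncounted and give no further data.
- The phrase stands for the research imaging. A subject whose stone was not seen has already been scanned, so is not before it, and the miss could stay.
- There is no such treatment, so the condition is never met and the sentence has no effect. The first sentence still permits discontinuation, and nothing says whether the subject is analysed.

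Taking the phrase to mean Group 2 surgery does not settle it, since Group 1 has no surgery. The text does not choose among these readings.

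**Step 2. Direction.** Take subjects with one stone on the comparator. Let S be true sensitivity (above 0 and below 1) and w the share of missed subjects removed under section 10.7. Neither is given in the protocol. Per subject with a stone:

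- detected and kept: S
- missed and kept: (1 − S)(1 − w)
- observed sensitivity = S / [S + (1 − S)(1 − w)] = S / [1 − w(1 − S)]

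If w = 0, the denominator is 1 and the observed value is S. For any w above 0, the denominator is below 1 and the observed value exceeds S. Removing misses can therefore only raise sensitivity.

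**Step 3. Limit.** If w = 1, observed sensitivity = S / [S + (1 − S) × 0] = S / S = 1. If every single-stone miss is removed, the result is 100% for any S above 0. Between w = 0 and w = 1 the protocol gives no input with which to place the bias.

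**Step 4. Several stones.** A subject with one stone seen and another missed need not be discontinued, so that missed stone can remain in the data. Per-stone sensitivity in multi-stone subjects is therefore affected less.

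**Step 5. With the fix.** Keeping every scanned subject sets w = 0, and the observed value returns to S as far as this mechanism is concerned.

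**The case against.** The strongest reply is that section 10.7 is permissive and may simply be wording that belongs to the related propulsion studies. Section 10.1 also describes testing a push pulse that an imaging-only study does not need. On that view there is a sentence to tidy up, not a planned exclusion. Moreover, stopping further collection deletes nothing already held: a Group 1 subject may already have both the CT and the scan saved.

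Much of this stands. A reader might infer that the protocol plans to exclude misses, and the text does not go that far. But the rule is in force as written, names the outcome under study as a ground for leaving, and says some of these subjects do not count. Data on file do not help if the subject is outside the enrolled set. If the wording does not belong to this study, that is a reason to correct it.

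A reader might also infer that the sonographer knew the CT result. The protocol does not support that:

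- The item order in section 5.1 is weak evidence, because the list is not strictly chronological: clinical follow-up images come before the 3D scan.
- Section 4.1 names the research team, not the sonographer. Section 4.7 says record data are not retained at pre-screening except for a compliance disclosure.
- No section makes the live operator's call the index test. Images, raw signals and video are saved, so an offline read fits equally well, and its rules may sit in a document not at hand.

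The order of reading is therefore a suggestion, not a demonstrated fault.

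**Conclusion.** The point holds for section 10.7. Its cut-off is undefined in an imaging-only study, and on one reading it removes the false negatives that questions 3 and 4 must count. If applied, the bias in sensitivity is upward. Its size cannot be stated: it depends on how often the permission is used and which reading is followed. It is zero if no scanned subject is dropped for this reason, and total in single-stone subjects if all such misses are dropped.

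The timing of the Group 1 call relative to the CT is secondary, because it rests on what the protocol does not say. A reader might further infer that specificity cannot be studied because everyone has a stone. That does not follow: second sides may be scanned in Group 1, and patients with only a ureteral stone can contribute stone-free kidneys.

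**What to change.** **Main change, section 10.7.** Reconcile the withdrawal text with the imaging-only statement in section 1.3, removing or defining the reference to an investigational treatment. State that any subject who was scanned remains counted, that the comparator is retained (CT in Group 1, surgical observation in Group 2), and that stones present on the comparator but not seen on ultrasound are analysed as misses. This concerns counting and data only; discontinuation for a subject's health or welfare is untouched.

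**Secondary suggestion, section 5.1, Group 1.** Base the detection analysis on a call recorded before the CT is opened, or on a read of the saved images masked to the CT with the audio muted. Acknowledge that masking is partial, since eligibility already tells the reader to expect a stone, and that a re-read cannot remove bias in where the operator searched.

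**Cost.** The main change is a wording amendment plus keeping comparator data on subjects already scanned, with no added patients or procedures. The secondary step costs either a change in when the CT is opened or some reader time. Reported sensitivity may look less favourable.

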	Department of Energy The research involves Department of Energy funding, facilities, data, or personnel.	ZIPLINE SUPPLEMENT: Department of Energy
	Drug, biologic, botanical, supplement Procedures involve the use of any drug, biologic, botanical or supplement, even if the item is not the focus of your research	ZIPLINE SUPPLEMENT: Drugs
	Emergency exception to informed consent Research that requires this special consent waiver for research involving more than minimal risk	ZIPLINE SUPPLEMENT: Exception from Informed Consent for Emergency Research (EFIC)
	Genomic data sharing Genomic data are being collected and will be deposited in an external database (such as the NIH dbGaP database) for sharing with other researchers	ZIPLINE SUPPLEMENT: Genomic Data Sharing

07/21/2025

х	Medical device Procedures involve the use of any medical device, even if the device is not the focus of your research, except when the device is FDA-approved and is being used through a clinical facility in the manner for which it is approved	ZIPLINE SUPPLEMENT: Devices
	Multi-site study (You are asking the UW IRB to review one or more sites in a multi-site study.)	ZIPLINE SUPPLEMENT: Participating Site in Multi- Site Research
	Participant results sharing Individual research results will be shared with subjects.	ZIPLINE SUPPLEMENT: Participant Results Sharing
	None of the above	
2 PARTICIPA	NTS	
2.1 Participants. Describe the general characteristics of the subject populations or groups, including age range, gender, health status, and any other relevant characteristics.		
Adult patients from the UW Urology clinic or the UW Kidney Stone Center at Northwest Hospital with at least one kidney stone and/or are being treated for nephrolithiasis (kidney and ureteral stones) with either lithotripsy or ureteroscopy (URS).		
	d exclusion criteria. Describe the specific criteria you will use to decide who we mong interested or potential subjects. Define any technical terms in lay langu	-

Inclusion criteria:

- Patients with at least one kidney stone and/or are being treated for nephrolithiasis with either lithotripsy or ureteroscopy (URS)
- Age 18 and up

Exclusion criteria:

- Inability to read the consent form
- Acute pain at the time of consent, which might impair the subject's decision-making at that time
- **2.3 Prisoners**. IRB approval is required in order to include prisoners in research, even when prisoners are not an intended target population.

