- Imaging procedure: We image the kidney(s), ureters and bladders of all subjects with the Verasonics research ultrasound device (with either C5-2 or P4-2 Philips ATL HDI commercial, clinical imaging probes both FDA approved). These subjects who are not undergoing surgery may also have additional imaging done with the Supersonic Imagine Aixplorer, a commercial clinical ultrasound (with the system's FDA approved imaging probes). All images from the devices will be saved as de-identified images for research purposes. We save the images and the raw electrical signals received from the probe and used to make the images. We capture the images through a screen capture program that builds all the image captures into a video. There is no video camera and no images of the subject taken; there is a video composed of the ultrasound examination. The video also captures the room audio this is used to "annotate" where we are in the kidney, what stone number we are looking at, etc. Nothing identifying the subject will be recorded, except it is possible the patient name may be recorded during this process. The ultrasound examination takes about 20-30 minutes per side.
- Images of stones taken by CT, ultrasound, or x-ray as part of clinical follow-up may be accessed in the medical record and saved. 3D images will not be placed in the medical record.
- We will use our prototype scanning device to perform a 3D imaging scan of the kidney. The prototype device uses a Verasonics research ultrasound imager with a standard clinical ultrasound imaging probe. The ultrasound imaging probe is secured in a rectangular frame that holds a motorized rotating ring, and our device performs a mechanically-operated 3D imaging scan of the kidney under computer control. The motorized rotating stage is a commercial product (RTHM-190, IntelLiDrives Inc., Philadelphia, PA). The sonographer will place the prototype 3D rotational imaging device at the same site was used for the 2D ultrasound scans. We will ask the subject to hold their breath for up to 10 seconds after inhaling while we perform the automated 3D ultrasound scan. We may repeat the procedure for quality assurance.

Group 2 – Subjects being treated by stone management surgery:

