- We will use our prototype scanning device to perform a 3D imaging scan of the kidney. The prototype device uses a Verasonics research ultrasound imager with a standard clinical ultrasound imaging probe. The ultrasound imaging probe is secured in a rectangular frame that holds a motorized rotating ring, and our device performs a mechanically-operated 3D imaging scan of the kidney under computer control. The motorized rotating stage is a commercial product (RTHM-190, IntelLiDrives Inc., Philadelphia, PA). The sonographer will place the prototype 3D rotational imaging device at the same site was used for the 2D ultrasound scans. We will ask the subject to hold their breath for up to 10 seconds after inhaling while we perform the automated 3D ultrasound scan. We may repeat the procedure for quality assurance.
- Magnetic tracking will not be used.
- **5.2** Data variables. Describe the specific data you will obtain (including a description of the most sensitive items). If you would prefer, you may upload a list of the data variables to the **Supporting Documents** SmartForm instead of describing the variables below.
 - Existing images of stones, audio annotated image videos, image raw data, size of stones, location of stones, number of stones, type of stones, treatment records, fluoroscopy images, endoscopic video images, the time shock waves were applied, number of shock waves applied, weight, height, race, age, sex and ethnicity.
- **5.3** Data sources. For all types of data that you will access or collect for this research: Identify whether you are obtaining the data from the subjects (or subjects' specimens) or whether you are obtaining the data from some other source (and identify the source).

If you have already provided this information in Question 5.1, you do not need to repeat the information here.

We are obtaining some data from the subjects and some data from the subjects' EMR.

- **5.4 Retrospective/prospective.** For all types of data and specimens that you will access or collect for this research: Describe which data are:
 - Retrospective (i.e., exist at the time when you submit this application)
 - Prospective (i.e., do not yet exist at the time when you submit this application)
 - Both retrospective and prospective (for example, past and future school records)

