Retrospective data: Existing images of stones weight, treatment records, height, race, sex and ethnicity Prospective data: audio annotated image videos, image raw data, fluoroscopy images, endoscopic video images, the time shock waves were applied and number of shock waves applied

Retrospective and Prospective data: images of stones, size of stones, location of stones, number of stones, type of stones,

5.5 Identifiability of data and specimens. Answer these questions carefully and completely. This will allow HSD to accurately determine the type of review that is required and to assist you in identifying relevant compliance requirements. Review the following definitions before answering the questions:

Access means to view or perceive data, but not to possess or record it. See, in contrast, the definition of "obtain". Identifiable means that the identity of an individual is or may be readily (1) ascertained by the researcher or any other member of the study team from specific data variables or from a combination of data variables, or (2) associated with the information.

Direct identifiers are direct links between a subject and data/specimens. Examples include (but are not limited to): name, date of birth, medical record number, email or IP address, pathology or surgery accession number, student number, or a collection of your data that is (when taken together) identifiable.

Indirect identifiers are information that links between direct identifiers and data/specimens. Examples: a subject code or pseudonym.

Key refers to a single place where direct identifiers and indirect identifiers are linked together so that, for example, coded data can be identified as relating to a specific person. Example: a master list that contains the data code and the identifiers linked to the codes.

Obtain means to possess or record in any fashion (writing, electronic document, video, email, voice recording, etc.) for research purposes and to retain for any length of time. This is different from **accessing**, which means to view or perceive data.

a. Will you or any members of your team have access to any direct or indirect identifiers?					
Yes → If yes, describe which identifiers and for which data/specimens. The study team will have access to direct identifiers: subjects' names, DOB, medical record number, email address, surgery accession number. The study team will also have access to the information that links between direct identifiers and the data.					
					No

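### Group 1 tests ultrasound against an undated CT in the medical record, with no rule on interval, choice of CT or intervening treatment or passage, so real stone change mixes with ultrasound error

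*Protocol*

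**What the plan says.** Section 1.5 of the Protocol poses accuracy questions. Question 2 is "How accurate is the measurement of stone size on ultrasound", question 3 is "How accurate is ultrasound at detecting stones", and question 4 asks about stones below 2 mm.

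For Group 1 (awake subjects), section 5.1 fixes the comparator: the aim is to see "how well ultrasound sees and sizes the stone, tested by comparison to CT in their" medical record. The same section adds two sources of record images:

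- Before the scan: "Existing CT, x-ray, ultrasound, or fluoroscopy images of the stone will be saved from the medical record".
- After the scan: "Images of stones taken by CT, ultrasound, or x-ray as part of clinical follow-up may be accessed in the medical record and saved".

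Section 2.2 admits adults who have a stone or are being treated by lithotripsy or ureteroscopy. It does not ask for a CT, for a recent CT, or for the absence of treatment since the CT.

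The variable list in section 5.2 begins "Existing images of stones, audio annotated image videos, image raw data, size of stones, location of stones, number of stones" and goes on to stone type and treatment records, among other items. It names no scan date and no spontaneous stone passage. Section 5.4 classes the stone data as "Retrospective and Prospective data: images of stones, size of stones, location of stones, number of stones, type of stones".

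Section 10.7 allows a subject to be discontinued when the stone cannot be found on ultrasound.

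**The concern.** An accuracy study needs the reference to show the stone as it was when the index test was done. Between a clinical CT and a later research ultrasound, a stone may pass, grow, form, shift position or be treated. Without a rule linking the two scans in time, a disagreement in Group 1 can mean that ultrasound was wrong or that the stone had changed, and the result does not separate the two. How much of each is present depends on how recently the clinic happened to order a CT. Enrolling more subjects does not remove this.

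At stake are the Group 1 estimates of detection and size error, and any statement about stones under 2 mm that draws on Group 1.

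**Working it through.** The Protocol states no sample-size basis, accuracy target or rate of stone change, so there is no figure of its own to reproduce. The check is a reading of the text followed by an illustration.

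**Reading the sections together**

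| Element needed for a valid pair | Where it would be | What is there |
|---|---|---|
| A CT exists | 2.2, 5.1 | Not required; the saved record images may be of other types |
| Maximum CT-to-ultrasound interval | 5.1 | None |
| Which CT, if several | 5.1 | None |
| Handling of treatment between scans | 2.2, 5.1 | None; treatment records are collected (5.2) but no rule uses them |
| Handling of passage between scans | 2.2, 5.1, 5.2 | None; passage is not a listed variable |
| Scan dates | 5.2 | Not listed |
| Stone not seen on ultrasound | 10.7 | Subject may be discontinued |

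**Detection (all inputs assumed).** Let true sensitivity for stones still present be 0.90, and let p be the share of CT stones gone by the ultrasound date. Take 100 CT stones, one per subject. Then 100 × (1 − p) are present and 90 × (1 − p) are seen.

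- If every unseen stone counts as a miss: apparent sensitivity = 0.90 × (1 − p).
- If every subject with an unseen stone is discontinued: only seen stones remain, so apparent sensitivity = 100%.
- With the correct denominator (stones still present): 90%.

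| p | Present | Seen | All unseen counted as misses | All unseen discontinued |
|---|---|---|---|---|
| 5% | 95 | 85.5 | 85.5% | 100% |
| 10% | 90 | 81 | 81% | 100% |
| 20% | 80 | 72 | 72% | 100% |

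At p = 10%, the same data can read anywhere from 81% (81/100) to 100% (81/81) around a true 90% (81/90), depending on how an unrecorded mix of lost stones and true misses is handled.

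**Size (all inputs assumed).** Let the SD of the ultrasound-minus-CT difference be 1.5 mm when the stone has not changed. Suppose true change between the scans has mean m and SD s, independent of measurement error. Apparent bias shifts by m, and the 95% limits-of-agreement half-width is 1.96 × √(1.5² + s²).

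- No change: 1.96 × 1.5 = 2.94 mm.
- m = 0.5, s = 0.5: bias shifts by 0.5 mm; 1.96 × √2.50 = 3.10 mm.
- m = 1, s = 1: bias shifts by 1 mm; 1.96 × √3.25 = 3.53 mm.

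Growth after an earlier CT makes ultrasound appear to oversize. With a later CT as reference, the sign reverses.

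**The case against.** The other side has several good points.

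- **Treatment is recoverable.** A reader might infer that affected pairs can never be identified. That goes too far: section 5.2 lists treatment records, so a CT that predates a lithotripsy can be found, and scan dates may be recoverable from the source records. What remains is that no rule uses those records, and that spontaneous passage is not listed at all.
- **No scoring rule is written.** A reader might infer that a vanished stone is scored as a miss and that sensitivity is therefore biased down. The Protocol says neither. Under section 10.7 the subject may instead be discontinued, which would also remove true misses and push sensitivity up.
- **Group 1 is defined by having stones.** A patient whose only stone is known to have passed or been removed is not plainly eligible. The problem therefore lies mainly with unrecognised passage, subjects with several stones, and growth or new stones. This narrows the point without removing it.
- **Follow-up CT.** Section 5.1 says that later images may be saved, not that they serve as the comparator. Their use as reference is only an inference. The gap exists on prior CT alone.
- **Group 2.** There the comparison is with the stone observed at surgery and imaging takes place during the procedure. A reader might take questions 2 to 4 as compromised throughout, but the documents support this for Group 1 only.
- **This belongs in an analysis plan.** A separate plan, not shown here, could hold a pairing window. That is fair for the window itself. The reference standard, entry criteria and collected variables are, however, fixed in this document, and a later plan cannot supply passage events that were never recorded.

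**Conclusion.** The point holds for Group 1. The reference is fixed as a CT in the record, and nothing in sections 2.2, 5.1, 5.2 or 5.4 ties that CT to the date of the research ultrasound or deals with stones treated or passed in between. The Group 1 part of questions 2 to 4 therefore measures ultrasound error together with stone change.

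The direction of the bias in sensitivity is not established, because the treatment of unseen stones is left open between counting and discontinuing. The size is unknown. The fall from 90% to 85.5%, 81% or 72%, and the widening of the limits of agreement from 2.94 mm to 3.10 or 3.53 mm, rest wholly on assumed inputs and show only that modest change between scans would matter. If nearly all Group 1 CTs turn out to be close in time to the ultrasound with no intervening events, the effect would be small; the Protocol neither ensures this nor lists scan dates with which to show it.

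**What to change.** - **Section 5.1:** count a Group 1 kidney in the accuracy comparison only if a CT falls within a prespecified window of the research ultrasound. A window of 60 or 90 days would be an example; both are assumed values, and the team should justify its choice.
- **Reference CT:** name the CT closest in time to the ultrasound as the reference, with the same rule for any follow-up CT.
- **Intervening events:** exclude kidneys with documented stone treatment or reported passage between the two scans, using the treatment records already collected.
- **Unseen stones:** keep subjects whose stone is on a qualifying CT but not seen on ultrasound in the detection analysis, and align section 10.7 with this.
- **Section 5.2:** add CT date, ultrasound date and reported stone passage.
- **Subjects already enrolled:** apply the same rule, as far as their records allow.

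The cost is a short rule, a sentence in 10.7 and three extra fields; staff already pre-screen the records (section 4.1). Subjects with an old CT or no CT can still be imaged but leave the accuracy comparison. If a fraction f of pairs is lost, standard errors rise by a factor of about 1/√(1 − f).
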